11.3 Investigator Assurances

Prior to initiating the study, the Principal Investigator at each study site will sign a protocol signature page, providing assurances that the study be performed according to the standards stipulated therein. The original signed copy of this document will be maintained in the site's regulatory binder and a copy will be sent to the DCC.

11.4 Laboratory Accreditation

The Principal Investigator must maintain documentation of adequate licensure or accreditation for all clinical laboratory facilities used for study sample analysis. In addition, the clinical laboratory's normal values for test results must be forwarded to the DCC prior to study initiation and annually thereafter. This documentation should cover the entire period the protocol is active.

11.5 Sponsor Monitoring/On-site Monitoring

The progress of the study may be monitored by an experienced site-monitoring firm, subject to sponsor funding availability, for compliance with applicable government regulations and protocol. These individuals will have access to all records necessary to ensure integrity of the data and the regulatory documents at the clinical sites.

11.6 Compliance with Agencies

The sponsor will ensure that this study is performed in compliance with applicable regulations associated with the Food and Drug Administration (FDA), the International Conference on Harmonization (ICH),²⁶ and the Declaration of Helsinki. The sponsors will

also keep a 1572 (Statement of Investigator), and current CVs of all Principal Investigators and Research Coordinators on file.

11.7 Record Retention

The DCC must maintain all trial records for a period in accordance with their internal Standard Operating Procedures (SOP) and applicable regulations. The Clinical Site must retain source records, including original Patient Consent Forms, until either the sponsor or DCC notifies them in writing.

11.8 Direct Access to Source Documents

Investigators will maintain, on-site, in an orderly fashion, for a period of no less than seven (7) years, and make available to the sponsor or the sponsor's representative, the following documents: the signed study protocol, amendments, informed consent documents, investigator brochure, approval letters from the IRB, drug accountability forms, CRFs, all primary source documentation, and all letters of correspondence.

11.9 Data Management and Quality Assurance

The Data Coordinating Center (DCC) will coordinate all study activities pertaining to:

- Design, development, production, testing and distribution of case report forms (CRFs) over the internet to the client workstations at each clinical center
- Collection, entry, verification, validation and query resolution of data
- Quality Assurance monitoring and reporting

Data management issues, especially those concerning data quality and integrity in multi-center trials, as discussed extensively in Meinert²⁷ DeMets²⁸ Neaton²⁹ Bailey³⁰, and McFadden³¹, will be addressed within the Manual of Procedures (MOP) and emphasized during the Research Coordinator (RC) training prior to protocol initiation.

The DCC will develop and maintain a computerized Data Management System (DMS) for this Protocol that will be deployed over the WORLD WIDE WEB using standard Web Browser tools on client workstations within each of the Clinical Centers. Case report forms (CRFs) will be available to be printed locally at the clinical centers from Portable Document Files (PDF). Originals of these forms will be retained by the Clinical Sites. Double data entry will be performed at the Clinical Centers, utilizing the DMS tools available on the clients' workstations. There will be a manual back-up system for implementing randomization of participants, in the event the DMS system is not functional at the moment that a new randomization is required.

Validation checks will be performed at the centralized database to verify data accuracy and identify missing, unclear, illogical, or problematic responses. Queries will be generated to resolve discrepancies. Confidentiality will be strictly adhered to by assigning a unique participant identifier that will not identify the subject by name. The Manual of Procedures will define these processes in detail.

12.0 Statistical Considerations

12.1 Summary of Study Design

The proposed study design is a two-arm, double blind, randomized clinical trial (RCT) to evaluate the efficacy and safety of pregabalin, as compared to matching placebo. The primary endpoint on which sample size requirements are based is the comparison of response rates, with responder being defined in terms of a decrease in the NIH-CPSI total score as described in Section 2.6. The proportion of “responders” in each treatment arm will be compared, in an intent-to-treat analysis, to evaluate the overall efficacy of the active therapy as compared to placebo. Approximately 318 eligible participants, 212 in the active treatment arm versus 106 in the placebo arm, will be randomized and followed for a period of six (6) weeks after randomization for the primary, and all secondary endpoints analyses.

An open-label phase for this trial (Phase II) will be offered to all participants after completion of the initial six (6) weeks of treatment, with the exception of those having a Serious Adverse Event while on study treatment in Phase I. Participants on active therapy or placebo will be offered active therapy and followed for an additional six (6) weeks. Participants will remain blinded to their initial treatment assignment until the end of the open label phase. The Phase II study is for the purpose of evaluating long term treatment effect. The GRA, NIH-CPSI will be re-examined again at the end of the Phase II.

An overview of the design considerations and statistical analysis plan, including sample size and power considerations, is provided in the following sections. Additional details will be provided in the study Data Analysis and Monitoring Plan (DAMP), provided prior to study initiation.

12.2 Sample Size Calculations

The primary analysis on which sample size requirements are based is the comparison of response rates, with responder being defined as 6 or more points of decline in the NIH-CPSI total score from baseline to primary endpoint. For this comparison, we desire adequate numbers of participants to detect a response rate of at least 60% in the active treatment arm versus 40% in placebo (difference of 20%). The estimated response rate of 40% for the placebo group is based on a previous CP/CPPS study (unpublished data). Assuming 90% power to detect the specified difference between the active treatment and placebo arms at a two-sided $\alpha = 0.05$ level of significance, a total of 318 participants are required. With the allocation ration to be 2:1, 212 participants will be randomized to the active treatment arm, and 106 to the placebo arm. This proposed sample size is adjusted for one planned interim analysis to be conducted when one half of the participants complete primary endpoint of Phase I. It also includes 10% inflation to account for clinical center variation in response rates.

Response Rate			Total Sample Size		Sample Size Per Arm	Per Center over 15-month	
Placebo	Pregabalin	Difference	Unadjusted	Adjusted	(Pregabalin/Placebo)	Total	Per Month
40%	55%	15%	516	570	380/190	52	3.5
40%	60%	20%	287	318	212/106	29	2
40%	65%	25%	181	201	134/67	18	1.2

12.3 Randomization and Stratification

To ensure balance across treatment groups within each Clinical Site, a stratified randomization will be used. Within each of the eleven strata defined by Clinical Site, subjects will be randomly allocated in equal proportions to the two treatment arms using a permuted block randomization procedure with variable block sizes of 3, 6 and 9. The variable block size will assure that neither participants nor their physicians will know the participant's location in the block.

We have chosen not to stratify the randomization scheme by any other variable than Clinical Site. This variable was chosen to control for factors unique to each clinic site, such as the characteristics of that site's participant population. While there clearly are other variables that will be observed and recorded before randomization, and which could be used for stratification, including participant's medical history or severity of symptoms, researchers are divided over the wisdom of stratification at the time of randomization on factors other than study site. Most importantly, stratification by multiple variables would likely result in small numbers per group and a fairly large chance of departure from the desired allocation ratio. Additionally, the usefulness of stratification is a function of how well the variable is related to the outcome measure.²⁷ There are no data to suggest that any of the potential stratification variables for this trial would be associated with achieving response in this study. However, a careful analysis will be carried out at the end of the trial to ensure that this is the case. Analysis procedures primarily involving regression methods will be used to adjust for any baseline group differences as discussed further below.

In order to maintain blinding, both the active drug and placebo will have an identical appearance. The treatment assignment code, corresponding to each treatment identifier number, will be known only to the person serving as the Data Coordinating Center Quality Assurance Director, until the completion of treatment and data collection on all participants. This information may also be known to the dispensing pharmacists at each institution, or a related centralized dispensing group. The study participants, and all other members of the investigative team, will remain blinded to the treatment assignment, including the investigators, the study nurses, and referring physicians. The biostatisticians will only be provided with the treatment assignment for placebo by the DCC Quality Assurance Director. At the end of a participant's study phase, the subjects and the treating physicians will be asked to guess their treatment groups, and provide the basis for their judgments for analysis later, to determine whether the blinding has been broken. However, except in the case of emergency unmasking, the treatment codes will not be identified until the DSMB has approved unblinding in preparation for the public dissemination of results.

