10.0 Adverse Events and Participant Withdrawals

The Investigator(s) will be required to provide appropriate information concerning any findings that suggest significant hazards, contraindications, adverse events, or precautions pertinent to the safety of the drug under investigation. Details of pre-existing conditions and adverse events reporting are described below.

Definition of Pre-existing Condition

A pre-existing condition is any chronic or acute sign, symptom, illness, or condition that the participant has at the time of entering the clinical trial; with the exception of those associated with the disease under study.

Definition of Adverse Events (AEs)

An adverse event is any unfavorable and unintended sign, symptom, or disease temporarily associated with the use of a medicinal product, whether or not considered related to the medicinal product.²⁴ The term “adverse event” could include, but not be limited to, any of the following events, which develop or increase in severity during the course of the study:

- Any signs or symptoms whether thought to be related or unrelated to the condition under study
- Any clinically significant laboratory abnormality
- Any abnormality detected during physical examination

The following data will be recorded on the appropriate case report forms (CRFs), regardless of whether they are thought to be associated with the study or the drug under investigation. (“Associated with the use of the drug” means that there is a reasonable possibility that the event may have been caused by the drug.)

- Any event reported by the participant, other than those expected and described in the treatment brochure, will be immediately reported to the treating urologist.
- Signs and symptoms will be graded by the Research Coordinator as mild, moderate, or severe as referenced by Common Toxicity Criteria (CTC) Standard (to be provided with the Manual of Procedures).

Adverse events will be addressed at each participant visit and as reported by the participant, a detailed description of the adverse event will be recorded on the Adverse Event CRF. Adverse Event CRFs will be reviewed regularly by the DCC and reports will be produced on a quarterly basis summarizing the adverse events by clinical center and masked treatment assignment.

All adverse events (clinical signs, laboratory values or other) must be followed until the return to normal or until stabilization of the patient conditions.

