12.10 Data Safety Monitoring and Interim Analysis

The study will be monitored routinely for issues of data quality, study conduct (including recruitment and follow-up rates), data quality, toxicity, and adverse events. One interim analysis will be performed approximately ten (10) months after the initiation of accrual, when approximately one third (n=106) of the participants will have been accrued and followed for six (6) weeks. The results of these analyses will be presented to the DSMB. The purpose of this interim analysis will be to compare the efficacy and safety of the active treatment relative to placebo. Both the primary endpoint and selected secondary efficacy endpoints, as well as safety, will be evaluated at the interim analysis. However, decisions regarding early closure (see below) will be based on the primary efficacy endpoint and generally not be considered based on the secondary endpoints.

To preserve the overall Type I error rate for the primary analysis of efficacy, group sequential boundary methods using the Lan and DeMets analog to O'Brien-Fleming boundaries³⁴ will be used to calculate the nominal significance levels to which the interim p-value is compared. Both upper (for differences in efficacy) and lower (for futility) boundaries will be used. Assuming 6 week data on 106 participants, corresponding to an information time of approximately 33%, the efficacy boundary significance level to which the observed p-value will be compared is 0.0002, and the futility boundary significance level is 0.993. A conditional power analysis may also be conducted at that time to provide additional information regarding early closure for futility. The final decision to terminate the trial early will be made by the DSMB. As mentioned, sample sizes have been adjusted to account for a very slight loss of statistical power due to the interim monitoring. The statisticians who conduct the interim analysis will not know the actual treatment assignments. The DCC Quality Assurance Director will provide these to the Chairperson of the DSMB in a sealed envelope. This envelope may be opened if deemed necessary by the DSMB.

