The table below outlines the proposed reporting schedule that will be used for this study. The abbreviations are as follows: CDM denotes clinical data management staff at the Data Coordinating Center (DCC); SC denotes the CPCRN Steering Committee, including all clinical site investigators, the DCC, and NIDDK representatives; and IRB indicates the local Institutional Review Boards for the Clinical Sites and DCC. The reports indicated as occurring every 3 to 4 months are generated to correspond to meetings of the Steering Committee.

Type of Report	Prepared By:	Provided To:	Frequency:
Serious Adverse Events (SAEs)	Sites, DCC	SC, DSMB, IRBs	Immediately
Participant Recruitment/Targets	CDM, Biostat	SC	q 4 weeks
Data Quality, Timeliness	CDM	SC, DSMB	q 3-4 mos
Demographics (combined)	CDM	SC, DSMB	q 3-4 mos
Adverse Events (combined)	Biostat	SC, DSMB	q 3-4 mos
Interim Analysis: Safety only	Biostat	DSMB	q 6 mos
Interim Analysis: Safety, Efficacy and futility	Biostat	DSMB	33% accrual, follow-up for 6 weeks after randomization
Final analysis: Safety and Efficacy	Biostat	DSMB	100% accrual, follow-up for 6 & 12 weeks after randomization

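### Section 12.3 gives the biostatisticians the placebo assignment, which in a two-arm trial is every assignment and contradicts the masking of the interim statisticians stated in 12.10

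*Combined protocol and SAP*

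**What the plan says.** Section 12.1 describes a double-blind trial of pregabalin against matching placebo, with two arms. Section 12.3 then makes several statements about who knows the assignments:

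- The code "will be known only to the person serving as the Data Coordinating Center Quality Assurance Director", until treatment and data collection are complete. Dispensing pharmacists or a central dispensing group may also know it.
- Participants and "all other members of the investigative team, will remain blinded to the treatment assignment".
- "The biostatisticians will only be provided with the treatment assignment for placebo by the DCC Quality Assurance Director". No time is given for this disclosure.
- Emergencies apart, codes are not to be identified before the DSMB has approved unblinding.

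Section 12.10 says of the interim: "The statisticians who conduct the interim analysis will not know the actual treatment assignments". It continues: "The DCC Quality Assurance Director will provide these to the Chairperson of the DSMB in a sealed envelope". The DSMB may open the envelope if it sees the need. The reporting table in the same section lists the biostatistics group as preparing the six-monthly safety interims, the efficacy and futility interim, and the final analysis. No separate unblinded statistician is described.

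On adverse events, Section 10.0 says that "reports will be produced on a quarterly basis summarizing the adverse events by clinical center and masked treatment assignment", without naming recipients. The reporting table in 12.10 gives the Steering Committee adverse-event data combined across arms.

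**The concern.** Sections 12.3 and 12.10 cannot both be followed. The word for limiting the disclosure to placebo suggests that something is withheld. With only two arms, nothing is.

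What is at stake is whether the trial can say that its analysts were masked. Section 12.5 allows methods to be revised and added as the detailed analyses are developed, and sets no end date. Some choices are open in the text available:

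- The NIH-CPSI is taken at both screening visits, and Section 12.7 does not say which is baseline.
- The prognostic factors for adjustment are given by example only.
- Missing-item rules are spelled out for the pain score alone.
- The GRA is placed at 12 weeks in Section 5.2 and at 6 weeks in 12.8.

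Under Section 12.3 as written, these could be settled by people who know the arms.

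**Working it through.** **1. The statements side by side**

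| Place | Who | Knowledge of assignments |
|---|---|---|
| 12.3 | Quality Assurance Director (possibly dispensers) | Full, as sole holder of the code |
| 12.3 | Biostatisticians | Placebo assignment, no timing |
| 12.3, end | Everyone else | None before DSMB approval, emergencies excepted |
| 12.10, text | Statisticians running the interim | None; sealed envelope to the DSMB Chairperson |
| 12.10, table | Biostatistics group | Prepares the interim and final analyses |

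The second and fourth rows concern the same group, because the table makes the biostatistics group the authors of the interim.

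**2. What the placebo assignment discloses.** If it is a list of participants, the pregabalin group is all randomized participants minus that list. If it is the label of the placebo arm, there are 2! = 2 ways to match two labels to two treatments, and naming placebo leaves 1. Either way, an analyst holding participant-level data knows every arm. With three arms there would be 3! = 6 matchings, and naming placebo would leave 2, so the active arms would stay masked from each other. This trial has no such remainder.

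**3. Would neutral codes repair it?** The inputs are 318 participants and 2:1 allocation (Sections 3.2 and 12.2), and an interim at 106 participants (12.10).

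- The plan's own figures reproduce: 318 × 2/3 = 212, 318 × 1/3 = 106, and 106/318 = 0.333, against the stated 33%.
- Expected interim groups: 106 × 2/3 = 70.7, about 71; 106 − 71 = 35.
- Chance that the active group is not the larger, under simple 2:1 allocation: P(X ≤ 53) with X ~ Binomial(106, 2/3) = 0.0003.
- With permuted blocks of 3, 6 and 9 within site, and participants spread at random over 10 or 11 sites (Section 3.2 gives ten, 12.3 gives eleven), the active group was the larger in all 20,000 simulated trials for each site count. The smallest active share seen was 0.604 (64 of 106) with 10 sites and 0.594 (63 of 106) with 11.

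Neutral labels would therefore reveal themselves in any by-arm interim table. Section 12.10 also describes an upper boundary for efficacy (0.0002) and a lower one for futility (0.993). A two-sided p-value could be computed without knowing the direction, but saying which boundary was crossed requires knowing which group is active.

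These counts assume 2:1. Section 12.3 also speaks of equal proportions, but blocks of 3 and 9 cannot be split equally, and Sections 3.2, 12.1 and 12.2 all give a 2:1 split. Steps 1 and 2 do not depend on the ratio.

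**4. Effect on design figures.** None. Sample size, power and alpha do not depend on who holds the code.

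**The case against.** The strongest reply is that the damage is limited and partly covered. Section 12.1 promises a Data Analysis and Monitoring Plan (DAMP) before initiation, and Section 12.11 has the DSMB review it by then. Section 12.7 fixes the responder definition and the exact Mantel-Haenszel test, and with 12.4 it counts withdrawals as non-responders. All of this stands and narrows what an unmasked analyst could change. It does not close the gap, because Section 12.5 still allows revision. The DAMP is not among the documents, so it may settle some of the open choices.

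It can also be said that Section 12.3 gives no timing, so the disclosure may have been meant for a late stage. Nothing in the text says so, and once unblinding has been approved there would be no reason to limit the disclosure to placebo. Nor is an analyst who knows the arms a defect in itself: someone has to prepare by-arm output for the DSMB. The defect is that the plan denies this and describes no separation of roles.

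A reader might infer two stronger things, and the documents support neither:

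- **That the whole trial is unblinded.** Section 12.3 keeps participants, investigators, study nurses and referring physicians masked.
- **That the quarterly adverse-event tables unblind the sites and bias the outcome.** Section 10.0 names no recipients, and the table in 12.10 sends the Steering Committee combined data. A table headed 71 and 35 shows a reader which code is pregabalin, but not which participant is in which arm. The six-week NIH-CPSI is completed at a clinic visit (Section 9.5); the Phase I telephone contacts are at weeks 2, 4 and 7. What remains is a difference in wording between 10.0 and 12.10 that should be resolved.

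**Conclusion.** The contradiction is real. As written, Section 12.3 gives the biostatisticians all assignments, while 12.10 says the statisticians running the interim have none. Section 12.3 also conflicts with its own statements on who holds the code and when it is released. The plan claims a masking property that its procedures do not provide, and neutral codes would not supply it at 2:1.

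The disclosure is complete for the analysts and, on this text, goes no further than the coordinating center. The consequence is possible unmasked revision of methods. No bias is demonstrated and no numerical error is involved. The conclusion assumes that the biostatisticians of Section 12.3 are the biostatistics group in the reporting table, and that the disclosure is not deferred by some document not available here. The passages should be reconciled before any by-arm output is produced.

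**What to change.** - **Section 12.3:** delete the sentence on the placebo assignment. State that one existing coordinating-center statistician receives the codes and prepares all by-arm output for the DSMB, and takes no part in later revisions of the analysis plan or in data-review decisions. State that the other biostatisticians see pooled data only until the DSMB approves unblinding. Amend the sentence naming the Quality Assurance Director as sole holder of the code to include this statistician.
- **Section 12.10:** amend the masking and sealed-envelope sentences to match, so that they no longer say the interim is run without knowledge of the arms.
- **DAMP:** require that any revision after the first by-arm output be made only by masked statisticians.
- **Section 10.0:** restrict quarterly adverse-event reports by arm to the DSMB, and give combined data to everyone else. Show both in the reporting table.

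The cost is wording and a division of roles among statisticians already in place. The one downside is that the designated statistician is kept off plan revisions and data-review decisions.
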